The SRT will consist of at least one investigator and the following Gilead Sciences, Inc. (Gilead) study team members: the Gilead medical monitor, representatives from Drug Safety and Public Health (DSPH) and Biostatistics. Others may be invited to participate as members of the SRT if additional expertise is desired. The Gilead medical monitor serves as the chair of the SRT. Investigators whom have enrolled a subject into the cohort the SRT is evaluating is/are required to participate in the dose escalation/expansion decision.

The recommended dose of GS-5829 to be combined with fulvestrant in the Randomized Phase 2 Dose Expansion part of this study will be determined based on the data available in the Phase 1b Dose Escalation portion of this study and from studies GS-US-350-1599 and GS-US-350-1604. The recommended dose will not exceed the MTD identified by the Phase 1b dose escalation

from this study. At least 6 subjects should have already been treated and evaluated at that dose level prior to enrolling subjects in the Randomized Phase 2 Dose Expansion.

Dose Limiting Toxicity (DLT) Definition

A DLT is a toxicity defined below and considered possibly related to GS-5829 if occurring during the DLT assessment window (Day 1 through Day 28) in each combination therapy cohort:

[figure not shown]
- Grade ≥ 4 neutropenia (absolute neutrophil count [ANC] $< 500/\text{mm}^3$)
- Grade ≥ 3 neutropenia (ANC $< 1000/\text{mm}^3$) with fever (a single temperature of $> 38.3^\circ\text{C}$ or a sustained temperature of $\geq 38^\circ\text{C}$ for more than one hour)
- Grade ≥ 3 thrombocytopenia
- Grade ≥ 2 bleeding (e.g. gastrointestinal, respiratory, epistaxis, purpura)
- Grade ≥ 3 or higher non-hematologic toxicity, except:
 - Grade 3 nausea or emesis with maximum duration of 48 hours on adequate medical therapy
 - Grade 3 diarrhea which persists for < 72 hours in the absence of adequate medical therapy
- Grade ≥ 2 non-hematologic treatment-emergent adverse event (TEAE) that in the opinion of the investigator is of potential clinical significance such that further dose escalation would expose subjects to unacceptable risk
- Treatment interruption of ≥ 7 days due to unresolved toxicity

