5.3.1. Dose Adjustment of GS-5829

If at any time in the study, a subject experiences a toxicity consistent with a Grade 4 AE that is deemed to be related to GS-5829, GS-5829 treatment will be discontinued permanently, with the exception of Grade 4 neutropenia, thrombocytopenia, or alopecia. If a subject experiences non-hematologic Grade 3 toxicity consistent with a DLT (See Section 3.2), dosing with GS-5829 will be postponed until the toxicity is resolved to Grade 0 or 1 (as defined by the CTCAE, version 4.03) or returns to the subject's baseline value. If the toxicity resolves to Grade 0 or 1 or returns to the subject's baseline value within 28 days from the start of the event, the subject may resume dosing of GS-5829 at a dose that is at least one dose level lower after discussion with the Gilead medical monitor (See Table 5-1). If a subject has Grade 4 neutropenia, Grade 3 neutropenia with fever, or Grade 3 thrombocytopenia, GS-5829 should be interrupted for up to 28 days and/or until the toxicity resolves to \leq Grade 1. If the Grade 4 neutropenia or Grade 3 fever and neutropenia resolves within 4 days (7 days for Grade 3 thrombocytopenia), then the subject may resume dosing at the same dose. If the Grade 4 neutropenia or Grade 3 fever and neutropenia takes $>$ 4 days ($>$ 7 days for Grade 3 thrombocytopenia), but within 28 days to recover, then the dose of GS-5829 must be resumed at a lower dose. If the Grade 4 neutropenia, Grade 3 fever and neutropenia or Grade 3 or higher thrombocytopenia takes longer than 28 days to recover then GS-5829 must be permanently discontinued. Grade 4 thrombocytopenia observed at any time must be followed by a dose reduction.

If the recurrent toxicity is hematologic a second dose decrease is allowed (lowest dose allowed is 2 mg) in either total daily dose or by a change in schedule such that the total amount of GS-5829 administered over a 28 day period is decreased by at least 25%.

Table 5-1. Dose Reduction of GS-5829

HEMATOLOGICAL ADVERSE EVENTS	
Neutropenia	
Grade \leq 3 Neutropenia	Maintain current dose level and schedule.

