Grade 4 neutropenia (or occurrence of Grade \geq 3 neutropenia (ANC $<$ 1000/mm 3) with fever (a single temperature of $>$ 38.3°C or a sustained temperature of \geq 38°C for more than one hour) or infection	Hold dosing with GS-5829 until the toxicity is resolved to \leq Grade 1. If the toxicity resolves to \leq Grade 1 within 4 days, the subject may resume dosing of GS-5829 at the same dose. If recovery to Grade \leq 1 takes $>$ 4 days, but within 28 days, then the subject may resume dosing of GS-5829 at a dose that is at least one dose level lower after discussion with the Gilead medical monitor. Granulocyte colony-stimulating factor (GCSF) is allowed (but not concurrent with GS-5829)

HEMATOLOGICAL ADVERSE EVENTS

Thrombocytopenia

Grade \leq 2 Thrombocytopenia	Maintain current dose level and schedule.
Grade 3 Thrombocytopenia	Hold dosing with GS-5829 until the toxicity is resolved to \leq Grade 1. If the toxicity resolves within 7 days, the subject may either resume at the same dose or a dose with is one level lower or at an intermittent dosing schedule (at least 25% less GS-5829 in a 28 day dosing period) after discussion with the Gilead medical monitor. If the thrombocytopenia takes 7-28 days to recover then the subject must resume at a dose one level lower or at an intermittent dosing schedule after discussion with the Gilead medical monitor.
Grade 4 Thrombocytopenia	Hold dosing with GS-5829 until the toxicity is resolved to \leq Grade 1. If the toxicity resolves within 28 days, the subject may either resume at a dose with is at least one level lower, or at intermittent dosing schedule (at least 25% less GS-5829 in a 28 day dosing period) after discussion with the Gilead medical monitor.

NON-HEMATOLOGICAL ADVERSE EVENTS

Hepatic Adverse Events (elevations in ALT or AST and/or bilirubin)

Grade 1 (ALT/AST \leq 3 x ULN) (Bilirubin \leq 1.5 x ULN)	Maintain current dose level and schedule.
Grade 2 (ALT/AST $>$ 3-5 x ULN) (Bilirubin $>$ 1.5 - \leq 3 x ULN)	Maintain current dose level and schedule. Monitor ALT, AST, ALP, and bilirubin at least once a week.
Grade 3	Hold dosing until \leq Grade 2. Permanently discontinue if any Grade 3 or Grade 4 elevation in AST or ALT associated with a Grade 2 elevation in bilirubin
Grade 4	Permanently discontinue GS-5829

Non-Hepatic, Non-Hematologic Adverse Events

Grade \leq 2	No change in dosing required. Dosing may be interrupted until Grade \leq 1 or baseline

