Grade 3	Hold dosing until \leq Grade 1 and decrease dose by at least one dose level lower or at intermittent dosing schedule (at least 25% less GS-5829 in a 28 day dosing period) after discussion with the Gilead medical monitor.
Grade 4	Permanently discontinue GS-5829

For subjects only enrolled to Phase 2 part of the study: if a subject tolerates a reduced dose for $>$ 4 weeks, GS-5829 dose may be increased to the next higher dose level, at the discretion of the investigator and after discussion with Gilead medical monitor. Successive adjustments to progressively higher dose levels can be made at 4-weeks intervals up to the starting dose level.

If the toxicity does not resolve or return to baseline, or subject experiences a recurrence of the toxicity after restarting study drug at a lower dose or if the toxicity does not resolve within 28 days, study drug(s) GS-5829, exemestane (Group A Phase 1b) or fulvestrant will be permanently discontinued and the subject will return for an EOT and a 30-day Safety Follow-Up visit. If a subject who is randomized to the combination arm discontinues one study drug for any reason, such as toxicity the other study drug will be discontinued as well.

If the subject was not receiving GS-5829 at the time disease progression was documented (e.g., due to reversible toxicity), after discussion with the Gilead medical monitor, GS-5829 may be re-started if the criteria for resuming treatment are met and the investigator feels it is in the subject's best interest to do so.

If a subject develops a recurrence of the same Grade 3 or 4 hematologic or any non-hematologic toxicity that the investigator considers related to GS-5829 and is clinically significant at the lower dose, then the subject should be permanently discontinued from all study drug(s).

After the 28 day DLT period in the Phase 1b Dose Escalation and at any time in the Randomized Phase 2 Dose Expansion, in the event of a Grade 2 hematologic or non-hematologic toxicity the investigator considers related to GS-5829, GS-5829 may be interrupted per the investigator's discretion for a maximum of 28 days and resumed at either the same or a lower dose.

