7.2.2. Assessment of Severity

The severity of AEs will be graded using the CTCAE, Version 4.03 ([Appendix 4](#)).

For each episode, the highest severity grade attained should be reported.

If a CTCAE criterion does not exist, the investigator should use the grade or adjectives: Grade 1 (mild), Grade 2 (moderate), Grade 3 (severe), Grade 4 (life-threatening), or Grade 5 (fatal) to describe the maximum intensity of the AE. For purposes of consistency with the CTCAE, these intensity grades are defined in [Table 7-1](#).

Table 7-1. Grading of Adverse Event Severity

Grade	Adjective	Description
Grade 1	Mild	Sign or symptom is present, but it is easily tolerated, is not expected to have a clinically significant effect on the subject's overall health and well-being, does not interfere with the subject's usual function, and is not likely to require medical attention.
Grade 2	Moderate	Sign or symptom causes interference with usual activity or affect clinical status, and may require medical intervention.
Grade 3	Severe	Sign or symptom is incapacitating or significantly affects clinical status and likely requires medical intervention and/or close follow-up.
Grade 4	Life-threatening	Sign or symptom results in a potential threat to life.
Grade 5	Fatal	Sign or symptom results in death.

The distinction between the seriousness and the severity of an AE should be noted. Severe is a measure of intensity; thus, a severe reaction is not necessarily a serious reaction. For example, a headache may be severe in intensity, but would not be classified as serious unless it met one of the criteria for serious events listed in Section 7.1.2.

7.3. Investigator Requirements and Instructions for Reporting Adverse Events and Serious Adverse Events to Gilead

Requirements for collection prior to study drug initiation:

After informed consent, but prior to initiation of study medication, the following types of events should be reported on the case report form (CRF/eCRF): all SAEs, and AEs related to protocol-mandated procedures.

Adverse Events

Following initiation of study medication, collect all AEs, regardless of cause or relationship, until 30-days after last administration of study IMP must be reported to the eCRF database as instructed.

All AEs should be followed up until resolution or until the AE is stable, if possible. Gilead Sciences may request that certain AEs be followed beyond the protocol defined follow up period.

Serious Adverse Events

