7.5. Toxicity Management

Treatment-emergent toxicities will be noted by the investigator and brought to the attention of the Gilead medical monitor or designee. Whether or not considered treatment-related, all subjects experiencing AEs must be monitored periodically until symptoms subside, any abnormal laboratory values have resolved or returned to baseline levels or they are considered irreversible, or until there is a satisfactory explanation for the changes observed.

Grade 3 or 4 clinically significant laboratory abnormalities should be confirmed by repeat testing as soon as practical to do so, and preferably within 3 calendar days after receipt of the original test results. Any questions regarding toxicity management should be directed to the Gilead medical monitor or designee.

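### Table 5-1 orders a permanent stop for Grade 3 AST/ALT with Grade 2 bilirubin but states none when bilirubin reaches Grade 3

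*Protocol*

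**What the plan says.** Table 5-1 in Protocol Section 5.3.1 sets the GS-5829 dosing action for hepatic events, by grade, for AST/ALT and/or bilirubin. Grade 2 bilirubin is above 1.5 and up to 3 x ULN. Grade 2 AST/ALT is above 3 and up to 5 x ULN. The Grade 3 row holds dosing until Grade 2 or lower and then adds: "Permanently discontinue if any Grade 3 or Grade 4 elevation in AST or ALT associated with a Grade 2 elevation in bilirubin". The Grade 4 row is a permanent stop.

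The text before the table has its own rule for a non-hematologic Grade 3 toxicity of DLT type: "dosing with GS-5829 will be postponed until the toxicity is resolved to Grade 0 or 1", or until it returns to the subject's baseline. If that happens within 28 days, "the subject may resume dosing of GS-5829 at a dose that is at least one dose level lower", after discussion with the medical monitor. The text after the table adds a later backstop: "if the toxicity does not resolve within 28 days, study drug(s) GS-5829, exemestane (Group A Phase 1b) or fulvestrant will be permanently discontinued". It also requires discontinuation if the toxicity recurs at the lower dose.

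The DLT definition (Synopsis and Section 3.2) uses the same single-grade bilirubin wording for combined AST/ALT and bilirubin elevations.

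**The concern.** The stop rule names two grades for AST/ALT but only one for bilirubin. Because the table gives Grade 2 bilirubin an upper limit, a subject whose bilirubin goes above that limit no longer meets the condition as worded. Unless some other rule catches her, the written action becomes weaker as the liver injury becomes worse.

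A combined rise in transaminases and bilirubin is where a dosing table should leave least to interpretation. Liver events were also foreseeable. Protocol Section 1.2.3.1 reports a Grade 3 AST elevation as one of two DLTs among 3 subjects at 6 mg in GS-US-350-1599, and 6 mg is a planned dose level here. Section 1.4 lists raised hepatic enzymes among the known toxicities of fulvestrant. At stake is whether such a subject must stop or may be re-exposed.

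**Working it through.** No formula applies. The check reads each combination of grades against the rules in Section 5.3.1.

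**Step 1: the written action for each combination**

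| AST/ALT | Bilirubin Grade 2 | Bilirubin Grade 3 | Bilirubin Grade 4 |
|---|---|---|---|
| Grade 3 | Permanent stop (combined rule, Grade 3 row) | Hold; restart possible | Permanent stop (Grade 4 row) |
| Grade 4 | Permanent stop (both rules) | Permanent stop (Grade 4 row) | Permanent stop (Grade 4 row) |

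Five of six cells have a stated stop. Along the first row the action goes from stop to hold to stop.

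**Step 2: the boundary in numbers.** Table 5-1 prints no limits for Grade 3. AST/ALT of 6 x ULN is taken as Grade 3 because Grade 2 ends at 5 x ULN.

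- Bilirubin 2.9 x ULN: since 1.5 < 2.9 ≤ 3, this is Grade 2, and a permanent stop is stated.
- Bilirubin 3.1 x ULN: since 3.1 > 3, this is no longer Grade 2, and no permanent stop is stated.

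The uncovered cell is therefore AST/ALT above 5 x ULN with bilirubin above 3 x ULN, both below Grade 4.

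**Step 3: does another rule close the cell?**

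- *Restart rule before the table.* By the table's grades, Grade 0-1 means AST/ALT ≤ 3 x ULN and bilirubin ≤ 1.5 x ULN. Restart needs those values, or baseline, within 28 days and at a lower dose. This limits restart but permits it. The hepatic Grade 3 row itself is looser: it asks only for recovery to Grade 2 and names no dose reduction. Using the stricter text understates the gap.
- *28-day and recurrence rule after the table.* This stops treatment only after non-resolution or after the event has recurred on re-exposure. It does not apply at onset.
- *Section 7.5.* "Grade 3 or 4 clinically significant laboratory abnormalities should be confirmed by repeat testing as soon as practical to do so", preferably within 3 calendar days, and subjects with adverse events "must be monitored periodically until symptoms subside" or abnormal values resolve, return to baseline or are otherwise accounted for. This is monitoring, not a dosing action.
- *Section 3.5.* An adverse event or the investigator's discretion may lead to discontinuation. That permits a stop but does not require one.

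None of these orders a stop for Grade 3 with Grade 3.

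**Step 4: the DLT sentence.** The wording is the same, but the effect is small. The DLT list already counts Grade ≥ 3 "or higher non-hematologic toxicity, except" for stated nausea, emesis and diarrhea cases. A possibly related Grade 3 plus Grade 3 event in the 28-day window meets that criterion.

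**The case against.** The strongest reply is that a bare Grade 2 is naturally read as a threshold. A stop that applies at 2.9 x ULN and lapses at 3.1 x ULN would defeat its own purpose, and many investigators would stop treatment anyway. Section 5.3.1 is also loose elsewhere: its text on interrupting treatment names Grade 3 thrombocytopenia alone, although the table holds dosing for Grade 4 as well. The probable intent is accepted. Still, the protocol often marks a threshold explicitly, as in the DLT list and in the neutropenia row of the same table, and the stop sentence itself spells out two grades for AST/ALT.

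A second reply is that bilirubin falling from above 3 to 1.5 x ULN or below must pass through the Grade 2 range, and the rule does not say that the two elevations must share a date. That reading is open, but it depends on when blood is drawn, and the sentence does not say whether a value on the way down counts. The adverse event reporting rule in Section 7.2.2 points the other way: "For each episode, the highest severity grade attained should be reported". That would make the episode Grade 3, though it is not a dosing rule.

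The third reply is that nothing now depends on the point. The trial ended during dose escalation, all subjects are off drug with the safety follow-up visit done, and no deaths were reported (SAP Sections 1 and 7.1.6.2). This is right about urgency. It does not make the rule correct.

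**Conclusion.** The concern holds. Read as written, Table 5-1 gives the worse of two combined liver injuries the more lenient action, in one cell of six. It looks like a wording slip, not a deliberate choice.

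The conclusion rests on the grade limits printed in Table 5-1 and on reading Grade 2 as that bounded range. If the sentence is taken to mean Grade 2 or higher, the gap disappears, but the reader has to supply that meaning. The safeguards in Section 5.3.1 make re-exposure less likely without replacing a stated stop. How often the combination would occur cannot be judged from the documents. No subject remains at risk, and no estimate, power figure or planned analysis depends on the point. It should be corrected, without urgency.

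**What to change.** In the hepatic Grade 3 row of Table 5-1, require the permanent stop for Grade 3 or 4 AST/ALT with a bilirubin elevation of Grade ≥ 2. Make the same change in the DLT sentence in the Synopsis and in Section 3.2 so that the three places agree.

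The cost is one symbol in three places. No treatment decision or planned analysis changes.

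Whether any subject fell in this cell can be checked from output already planned. SAP Section 7.2.3 counts and lists AST or ALT above 3 x ULN with total bilirubin above 1.5 and above 2 x ULN on the same postbaseline visit date. A case in this cell has AST/ALT above 5 x ULN and bilirubin above 3 x ULN, so it exceeds every one of those limits and will appear there if both values share a date.

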1.4. Risk/Benefit Assessment for the Study

Based on the systemic concentrations of GS-5829 measured in the repeat dose toxicity studies in mice and dogs, the margins of exposure at the severely toxic dose in 10% of rodents (STD10) in mice and HINSTD in dog are approximately 6.3- and 1-fold, respectively, at the anticipated clinically efficacious exposure. Another bromodomain inhibitor in development has identified thrombocytopenia as the earliest signs of toxicity in human studies, a toxicity which may be easily monitored.

As of November 2016, a total of 40 subjects have been dosed with GS-5829 as monotherapy or in combination with standard of care through two ongoing studies: GS-US-350-1599 and GS-US-350-1604. The drug is generally well tolerated. Assessments for AEs and monitoring for laboratory abnormalities are specified in the protocol and include symptom and AE assessment on Days 1 and 15 of the first two 28 day cycles, Day 1 of the third 28 day cycle, and

then every 28 days until end of treatment (EOT) which will be followed by a 30-day Safety Follow-Up Visit. Physical examinations will occur on Day 1 of each 28-day cycle until EOT which will be followed by a 30-day Safety Follow-Up Visit.

The safety monitoring frequency is considered sufficient to identify potential AEs as they emerge. In addition, mitigation strategies are incorporated into the study design. The inclusion and exclusion criteria are designed to ensure subjects have acceptable organ function to be eligible for this study, such that confounding significant co-morbidities are excluded. Study medications will continue until disease progression, unacceptable toxicity, consent withdrawal, or subject's refusal of treatment.

Exemestane and fulvestrant have been approved for treatment of advanced breast cancer in postmenopausal women whose disease has progressed either following tamoxifen or anti-estrogen therapy. The known toxicities for exemestane for this patient population are hot flushes, nausea, fatigue, increase sweating, increased appetite ([Appendix 8](#)). The known toxicities for fulvestrant are increased hepatic enzymes (ALT, AST and ALP), injection side pain, nausea, bone pain, arthralgia, headache, back pain, fatigue, pain in extremity, hot flash, vomiting, anorexia, asthenia, musculoskeletal pain, cough, dyspnea and constipation ([Appendix 9](#)).

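### Possibly related Grade 2 bleeding on Days 1–28 is a dose-limiting toxicity, yet section 5.3.1 and Table 5-1 leave holding GS-5829 in that patient optional

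*Protocol*

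**What the plan says.** **DLT definition (protocol section 3.2).** An event that is possibly related to GS-5829 and occurs on Days 1–28 is a DLT if it meets a listed criterion. One criterion is Grade 2 or higher "bleeding (e.g. gastrointestinal, respiratory, epistaxis, purpura".

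**Patient dosing rules (protocol section 5.3.1).** The text links patient dosing to the DLT list, but only from Grade 3: "If a subject experiences non-hematologic Grade 3 toxicity consistent with a DLT (See Section 3.2), dosing with GS-5829 will be postponed". After recovery within 28 days, dosing resumes "at a dose that is at least one dose level lower after discussion with the Gilead medical monitor".

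Table 5-1 has hematological rows for neutropenia and thrombocytopenia, hepatic rows, and a block for everything else. The Grade ≤ 2 row of that last block reads "No change in dosing required. Dosing may be interrupted until Grade" ≤ 1 or baseline.

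A separate paragraph lets the investigator interrupt for related Grade 2 toxicity. It is discretionary, and its scope is "After the 28 day DLT period in the Phase 1b Dose Escalation and at any time in the Randomized Phase 2 Dose Expansion".

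**Rules that act later or more generally.** Section 5.3.1 states that "if the toxicity does not resolve within 28 days, study drug(s) GS-5829, exemestane (Group A Phase 1b) or fulvestrant will be permanently discontinued". Section 7.5 says "Treatment-emergent toxicities will be noted by the investigator and brought to the attention of the Gilead medical monitor or designee", with no deadline. Section 3.5 permits stopping for an adverse event but does not require it.

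**The concern.** The sponsor set the escalation threshold for bleeding lower than for most other toxicities, but the bleeding patient's own dosing did not follow. Bleeding is a risk that the documents themselves flag:

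- Dogs had alveolar hemorrhage at 0.1 mg/kg/day and above (section 1.2.2.2). That dose is the dog highest non-severely toxic dose, where section 1.4 puts the exposure margin at about 1-fold. Section 1.2.2.2 adds that the lung pattern was potentially consistent with pneumonia, although no bacteria were found.
- Section 5.4 says that the mechanism of bleeding is not understood, and prohibits anticoagulants.
- One adrenal hemorrhage DLT occurred on monotherapy at 4 mg, the starting dose of this study (section 1.3.1).
- SAP section 7.1.7.2 makes haemorrhage one of three adverse events of interest.

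At stake is continued exposure, at an unchanged dose, of a patient with a DLT of this kind, with no dosing decision required when it is found.

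**Working it through.** No sample-size or power figure enters, so the check sets each DLT criterion in section 3.2 beside the action in section 5.3.1 and Table 5-1.

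| DLT criterion (section 3.2) | Action at onset | Required? |
|---|---|---|
| Grade 4 neutropenia | Hold | Yes |
| Grade ≥ 3 neutropenia with fever | Hold | Yes |
| Grade ≥ 3 thrombocytopenia | Hold; Grade 4 also needs a lower dose or a reduced schedule | Yes |
| Grade ≥ 3 non-hematologic toxicity (with exceptions) | Grade 3 hold; Grade 4 permanent stop | Yes |
| Grade 3/4 AST or ALT with Grade 2 bilirubin (paragraph after the list) | Permanent stop | Yes |
| **Grade 2 bleeding** | **May interrupt** | **No** |
| Investigator-judged Grade 2 non-hematologic event | May interrupt | No, but the investigator making the judgement can hold |
| Interruption of 7 days or more | Already interrupted | Not applicable |

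For neutropenia and Grade 3 thrombocytopenia the text says dosing should be interrupted while Table 5-1 says to hold; I read this as required.

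**Which row catches Grade 2 bleeding.** The hematological block covers only neutropenia and thrombocytopenia, so bleeding falls by elimination into the non-hepatic, non-hematologic block. Calling it hematologic would not help, since no hematologic rule requires a hold for it at Grade 2.

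**Whether another passage requires a hold at onset.** None does. The hold for non-hematologic DLTs is limited to Grade 3. The discretionary Grade 2 paragraph starts, in Phase 1b, only after Day 28. The 28-day stop acts on non-resolution, not on onset. Cohort review is no substitute, because the dose–DLT model is run once all subjects in the cohort have at least 28 days of follow-up (section 3.2).

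**What the rules permit, as a ceiling.** Section 1.4 schedules "symptom and AE assessment on Days 1 and 15 of the first two 28 day cycles", so Day 15 is the only scheduled adverse event assessment between Day 1 and Cycle 2 Day 1. For a bleed found then, doses remaining in the cycle are 28 − 15 + 1 = 14, and 14/28 = 50%. All of these may be taken unchanged. This is what the text allows, not a forecast.

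**Cost of a hold.** One day: 1/28 = 3.6% of a cycle's doses. Six days: 6/28 = 21.4%.

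**Evaluability.** Section 6.12 counts a subject with a DLT before Day 28 as evaluable without 21 doses. A hold for such a DLT therefore does not remove the subject from the DLT analysis. A resulting interruption of 7 days or more adds no further DLT subject, because she is already counted.

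**The case against.** **It is a deliberate choice.** The DLT list steers cohort escalation and Table 5-1 steers the patient; a cautious escalation trigger need not compel a hold. It stands that this is a stated rule, not an internal contradiction: a site can follow both sections. But section 5.3.1 itself ties the patient's dosing to section 3.2 DLTs, so the two are not separate systems. The bleeding DLT is the one left without a required action where no judgement about dosing risk is built into the criterion.

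**Safeguards exist.** The investigator may interrupt or stop, and treatment continues only short of unacceptable toxicity (section 3.4). Entry requires INR ≤ 1.2 and platelets of at least 100 × 10⁹/L, and excludes recent bleeding, bleeding diathesis and anticoagulant or antiplatelet use. Blood counts and coagulation are checked on Cycle 1 Day 15. Section 7.5 requires periodic monitoring of adverse events. All of this stands and makes the gap small, but none of it is a required hold.

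**The dose counts are hypothetical.** Correct. The 14 doses assume that nobody uses the power to interrupt. A ceiling of 28 doses could be drawn from the 28-day stop, but that sentence follows the hold-and-restart rules, and whether it governs an event that was never held is a matter of reading.

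**A required hold has a pharmacokinetic cost.** Also correct. GS-5829 pharmacokinetics is the Phase 1b secondary endpoint, with intensive sampling on Cycle 1 Day 15. A hold spanning that day could lose one steady-state profile from a cohort of three.

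**The bleeding rationale does not end on Day 28.** This stands. A hold confined to the DLT window would be compulsory on Day 28 and optional on Day 29 for the same event, so the rule should apply throughout treatment.

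**Conclusion.** The point holds in limited form. For possibly related Grade 2 bleeding on Days 1–28, a hold is optional, whereas all criteria set at Grade 3 or above carry a required hold or stop. It is a cheap improvement for patient safety, not a flaw in the escalation design or the analysis.

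A reader might infer more than the documents support:

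- *That dosing must continue.* It need not; interruption and discontinuation are both allowed.
- *That escalation is compromised.* It is not; the event enters the dose–DLT model as a DLT.
- *That Grade 2 DLTs are mishandled in general.* The investigator-judged criterion also lacks a required hold, but the person who declares it can hold the drug. The substantive gap is bleeding alone.
- *That a rate can be given.* The only bleeding DLT reported is one adrenal hemorrhage among 27 evaluable monotherapy subjects, in another study, grade not stated. If it was Grade 3 or above, existing rules would cover it. No frequency is estimated.

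The conclusion assumes that Grade 2 bleeding belongs in the non-hepatic, non-hematologic block; as shown, it does not change if bleeding is classed as hematologic. SAP section 1 records that the study was discontinued during dose escalation with all subjects off drug, so the correction is to the protocol as written.

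**What to change.** Add one row to Table 5-1:

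*Grade 2 bleeding considered possibly related to GS-5829, at any time on treatment: hold GS-5829 until Grade ≤ 1 or baseline. If this takes 28 days or less, resume at the same or a lower dose level once discussed with the medical monitor. If longer, discontinue permanently.*

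Add *except bleeding (see bleeding row)* in two places: the Grade ≤ 2 non-hepatic, non-hematologic row, and the discretionary Grade 2 paragraph of section 5.3.1. The rule is then the same before and after Day 28. The hepatic rows, the Grade 3 and 4 rows and the handling of the investigator-judged Grade 2 criterion can stay as they are.

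The cost is one row and two short exceptions, with no new procedure. Hold with same-dose restart has a precedent in Table 5-1, for Grade 3 thrombocytopenia that resolves within 7 days. The downsides are a few missed doses for minor bleeds such as epistaxis and the possible loss of a Cycle 1 Day 15 profile. Same-dose restart keeps the first small.
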